### 2.6.1 Screening Assessments (within 28 days prior to start of treatment)

Written informed consent for participation in the study must be obtained before performing any study specific screening tests or evaluations. Informed Consent Forms (ICFs) for all patients screened (whether enrolled or not) will be maintained at the study site.

All screening and baseline assessments must be completed and reviewed to confirm that patients meet all eligibility criteria. An Eligibility Screening Form documenting the investigator's assessment of each screened patient with regard to the protocol's inclusion and exclusion criteria is to be completed and kept at the study site.

Screening assessments include medical history and concomitant medications, documentation of ATL diagnosis in accordance with the WHO revised classification [WHO 2008] and treatment history. Screening assessments will be performed within 28 days prior to Cycle 1 Day 1 (C1D1). A pretreatment bone marrow test (aspiration or biopsy) would be required. Results of standard-of-care tests or examinations performed prior to obtaining informed consent and within 28 days prior to C1D1 may be used (and do not need to be repeated for screening unless they do not meet the criteria defined in the protocol). Similarly, tumor assessment tests <2 weeks outside the 28-day window in the absence of clinical evidence of PD, the results may be accepted.

Women of childbearing potential must agree to practice contraceptive measures after signing informed consent. A negative serum pregnancy test will be obtained during screening.

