### **2.5 Selection of Study Population**

#### **2.5.1 Inclusion Criteria**

Patients may be entered in the study only if they meet **all** of the following criteria:

1. Histopathological, or cytological diagnosis of ATL confirmed as seropositive for anti-Human T-lymphotropic Virus type-I (HTLV-I) antibody
2. Acute, lymphoma or unfavorable chronic types. The unfavorable chronic type is defined by the presence of at least 1 of the following: serum albumin <3.5 g/dL, lactic dehydrogenase (LDH) >300 U/L or blood urea nitrogen (BUN) >25 mg/dL. The patient must have at least 1 of measurable lesion, or evaluable lesion in either of peripheral blood or skin.
3. Relapsed or refractory disease after receiving prior systemic therapy with mogamulizumab, or  $\geq 1$  prior systemic therapy with cytotoxic chemotherapy in case of intolerance/contraindication for mogamulizumab. And there is no other standard treatment which can be considered appropriate for patients.
4. Male or female, aged 20 years or older
5. Eastern Cooperative Oncology Group (ECOG) Performance Status of 0 to 2
6. Life expectancy of greater than 3 months
7. Meeting the following baseline laboratory criteria for screening:
  - a. Absolute Neutrophil Count >1500/ $\mu$ L independent of growth factor support within 7 days
  - b. Platelets >75,000/ $\mu$ L independent of transfusion within 14 days
  - c. Hemoglobin >8 g/dL independent of transfusion within 14 days
  - d. Serum creatinine <1.5  $\times$  upper limit of normal (ULN)
  - e. Serum aspartate aminotransferase/glutamyl oxaloacetic transaminase (AST/SGOT) and alanine aminotransferase/glutamyl pyruvic transaminase (ALT/SGPT)  $\leq 3 \times$  ULN
  - f. Serum bilirubin  $\leq 1.5 \times$  ULN
8. Negative serum pregnancy test for females of childbearing (reproductive) potential. Female patients of child bearing potential must use an effective method of birth control (e.g., hormonal contraceptive, intrauterine device, diaphragm with spermicide or condom with spermicide) during treatment period and 1 month thereafter. Males must use an effective method of birth control (2 barrier methods) during treatment period and 3 months thereafter.

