**2.5.2 Exclusion Criteria:**

Patients who meet **any** of the following criteria are **not** to be enrolled:

1. Patients in whom central nervous system lymphoma is recognized during screening (if suspected clinically, imaging study should be performed to confirm)
2. Male patients with QTcF >450 msec at screening, female patients with QTcF >470 msec at screening, or patients with congenital long QT syndrome, clinically significant arrhythmia, history of congestive heart failure (New York Heart Association Class III or IV) or acute myocardial infarction within 6 months of starting the study drug at screening.
3. Patients with known hypersensitivity to benzamide class of compounds or any of the components of HBI-8000 tablets, and patients with prior exposure of HBI-8000
4. Patients with a history of second malignancy other than disease under study. The exceptions are diseases (excluding diseases listed below) that have been treated with curative intent with no evidence of recurrence in past 5 years. Furthermore, if the second malignancy is one of the following diseases that were treated with curative intent, it is only required that there is no evidence of recurrence in past 2 years:
  - a. Basal cell carcinoma of the skin
  - b. Squamous cell carcinoma of the skin
  - c. Cervical carcinoma in situ
  - d. Carcinoma in situ of the breast
  - e. An incidental histological finding of prostate carcinoma (TNM Stage T1a or T1b)
  - f. Early-stage gastric cancer treated with endoscopic mucosal resection or endoscopic submucosal dissection
5. Autologous stem cell transplantation within 12 weeks (84 days) of starting the study drug
6. History of allogeneic stem cell transplantation
7. Organ transplantation recipients except autologous hematopoietic stem cell transplantation
8. Uncontrolled intercurrent infection
9. Hepatitis B surface antigen-positive, or hepatitis C virus antibody positive. In case hepatitis B core antibody and/or hepatitis B surface antibody is positive even if hepatitis B surface antigen negative, a hepatitis B virus DNA test (real-time polymerase chain reaction measurement) should be performed and if positive, the patient should be excluded from study
10. Any history of testing positive for human immunodeficiency virus or known acquired immunodeficiency syndrome
11. Uncontrolled diabetes mellitus, hypertension, endocrine disorder, bleeding disorder
12. Major surgery or radiation therapy within 28 days of starting the study drug

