13. Receiving investigational agents or anti-cancer therapy within 28 days, nitrosourea or mitomycin C within 42 days, of starting the study drug
14. Receiving antibody therapy for ATL within 4 weeks of starting the study drug
15. Women who are breastfeeding or women who are not willing to stop breastfeeding during study treatment period and for 30 days after the last dose of study drug
16. Potential for non-compliance or at increased risk based on investigator's judgement

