#### **2.6.2 Baseline Assessments on Cycle 1 Day 1 (C1D1)**

Baseline assessments include a complete physical examination, vital signs, ECOG performance status, weight, concomitant medications, laboratory tests (hematology, chemistry, coagulation, and urinalysis), and safety ECG. Women of childbearing potential must have a negative pregnancy status confirmed by serum test before dosing. If Serum pregnancy test result cannot be obtained on the same day before dosing, urine pregnancy test should be conducted additionally and the result should be confirmed before dosing (see [Appendix A](#)). Some of the pre-dose assessments except vital signs and ECG may be performed 1 day before C1D1 to accommodate scheduling requirements in the hospital.

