### **2.10.1 Prohibited Medications and Therapy**

The following drugs are prohibited.

- Drugs known to produce significant QT prolongation and ventricular dysrhythmias (see [Appendix E](#))  
Prohibited from signing informed consent through the EoT assessment
- Anti-cancer therapy other than study medication

Prohibited during the study and within the following time intervals prior to the first dose of study drug.

- 4 weeks for anti-cancer chemotherapy
- 6 weeks for nitrosourea and mitomycin C
- 4 weeks for anti-cancer monoclonal antibody therapy

Corticosteroid prescribed for medical conditions other than lymphoma is not considered as an anti-cancer therapy for this study, for example: chronic obstructive pulmonary disease for allergy, topical steroids for rash.

-Please note that patient use of any prohibited medication is considered a protocol violation. In the event of prohibited medication use, investigator should consult study medical monitor to define an appropriate course of action if needed.

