## **9.4 Appendix D: Tumor Response Criteria**

### **9.4.1 Method of Efficacy Assessment**

Overall response will be assessed based on evaluation at screening and post-dose evaluation including complete tumor response assessments (peripheral blood, skin lesions, nodal and extranodal lesions) and on Day 1 of subsequent cycles for peripheral blood and skin lesions. Imaging studies such as CT to evaluate nodal and extranodal lesions will be performed by end of the 4th week, the eighth week, then every 8 weeks ( $\pm$  1 week) from C3D1. However, if a patient develops clinical signs and symptoms of PD, or unacceptable toxicity occurs, tumor assessment may be performed sooner as needed. If a patient discontinues study treatment before PD is recorded, and if their last tumor assessment was  $>30$  days earlier from EoT visit, tumor assessment should be performed at EoT. In these patients, further tumor assessments are to be performed approximately every 3 months  $\pm$  2 weeks until PD or the start of new cancer therapy whichever occurs first, unless consent to study participation is withdrawn.

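### The screening exception lets a baseline scan predate the last prior therapy: scans are accepted from about day -41, while most therapy is barred only within 28 days

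*Combined protocol and SAP*

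**What the plan says.** **Scan timing.** Section 2.6.1 places screening within 28 days before Cycle 1 Day 1 (C1D1). It then allows an exception: "tumor assessment tests <2 weeks outside the 28-day window in the absence of clinical evidence of PD, the results may be accepted". The only condition is that there is no clinical sign of progression, and acceptance is optional.

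**Washout.** Section 2.5.2 excludes:
- exclusion 12: "Major surgery or radiation therapy within 28 days of starting the study drug";
- exclusion 13: "Receiving investigational agents or anti-cancer therapy within 28 days", with 42 days for nitrosourea and mitomycin C;
- exclusion 14: "Receiving antibody therapy for ATL within 4 weeks of starting the study drug".

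Section 2.10.1 repeats 4 weeks for chemotherapy and antibodies and 6 weeks for nitrosourea and mitomycin C, under the words "Prohibited during the study and within the following time intervals prior to the first dose of study drug".

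**Use of the scan.** Appendix D, section 9.4.1, states: "Overall response will be assessed based on evaluation at screening and post-dose evaluation including complete tumor response assessments". Section 9.4.2.1.6 fixes the screening sum of bidimensional products, and section 9.4.3.1.1 uses it as the denominator of the reduction rate. Section 9.4.2.1.1 asks only that the CT come before study drug. No section requires it to follow the last prior therapy.

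**C1D1.** Section 2.6.2 states: "Baseline assessments include a complete physical examination, vital signs, ECOG performance status, weight, concomitant medications, laboratory tests". The rest of its list contains no tumor assessment, and the Schedule of Events shows none at that visit.

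**The concern.** The ordinary window and the 28-day washout fit together: any permitted prior therapy ends before an in-window scan is taken. The exception moves the scan limit back by up to 13 days but leaves the washout where it is. A permitted treatment can then fall between the reference scan and the first dose of HBI-8000.

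The condition attached to the exception does not address this. It screens out growth, whereas the problem is shrinkage. There is no control arm to absorb such shrinkage, so it would enter the primary endpoint, ORR, as an effect of HBI-8000. With 18 evaluable patients, one response can decide whether the exact interval excludes 5%.

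**Working it through.** **1. The plan's own figure.** Section 5.2 gives a 5% reference rate, a 30% target, two-sided alpha of 5%, 18 patients and 80% power. With an exact binomial test and an upper tail of at most 2.5%, the rule at n = 18 is at least 4 responses:
- P(X ≥ 4 | 18, 0.05) = 1.09%;
- P(X ≥ 4 | 18, 0.30) = 83.5%. At n = 17 the power is 79.8%, so 18 is consistent with an 80% target;
- the exact 95% lower limit is 3.6% for 3/18 and 6.4% for 4/18.

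The 4-of-18 rule is derived here from the power statement. The plan does not write it down.

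**2. Day arithmetic.** Fewer than 14 days outside a 28-day window means at most 28 + 13 = 41 days before C1D1. Therapy is permitted on day -29 or earlier. After a day -41 scan, permitted therapy can fall on days -40 to -29, which is 12 days. An in-window scan (day -28 or later) leaves no such day. Nitrosourea and mitomycin C (42 days) and autologous transplant (84 days) are not exposed.

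**3. Effect on the PR threshold (target lesions only).** PR needs a reduction of at least 50% from the screening sum. If the sum has already fallen by a fraction s at C1D1, the further reduction needed is 1 - 0.5/(1 - s):

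| Shrinkage before C1D1 | Further reduction needed for PR |
|---|---|
| 0% | 50% |
| 10% | 44.4% |
| 20% | 37.5% |
| 30% | 28.6% |

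Illustration: 20 cm² on day -41, 16 cm² at C1D1 and 9.8 cm² at week 4.
- From the accepted scan: (20 - 9.8)/20 = 51.0%, in the PR range.
- From C1D1: (16 - 9.8)/16 = 38.8%, not PR.

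Growth works the other way. With 20% growth before C1D1, the reduction needed is 1 - 0.5/1.2 = 58.3%.

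**4. Illustrative scale for ORR.** The documents do not say how many patients would use the exception or how often a response would carry over. Assume m exposed patients, each with response probability 0.05 + 0.95q, where q is the carry-over chance, and 18 - m patients at 0.05. Then P(at least 4 responses) is:

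| m | q = 10% | q = 30% | q = 50% |
|---|---|---|---|
| 1 | 1.48% | 2.27% | 3.06% |
| 2 | 1.97% | 4.35% | 7.52% |

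The nominal 2.5% is passed only when q exceeds about 36% (m = 1) or 15% (m = 2). A q of 50% is extreme, since it exceeds the 30% target for the study drug itself. In the opposite direction, if growth halves the response chance in 1 or 2 patients (0.15 instead of 0.30), power falls from 83.5% to 81.7% or 79.6%.

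**5. What the table does not show.** It compares carry-over with no carry-over. Therapy on day -29 followed by a scan on day -28 is allowed under the ordinary window, and most of that therapy's effect would come after the scan. The table therefore does not isolate the part due to the exception.

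**The case against.** The strongest reply is that existing rules leave few such patients and that the fix does not remove carry-over.

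- **Rarity.** Criterion 3 of section 2.5.1 requires relapsed or refractory disease and that "there is no other standard treatment which can be considered appropriate for patients". A patient clinically failing the intervening therapy loses the exception, and one shrinking on it must still qualify. Anti-cancer therapy is barred during the study, so scan and therapy would mostly both be standard care before consent. Acceptance is discretionary. All this stands and makes the case uncommon. None of it dates the scan, because criterion 3 describes disease status and is not tied to the most recent therapy.
- **Independent review.** Sections 3.4.2 and 3.4.3 apply the same criteria to each patient's sequential data. Nothing there tells the reviewers to reject a baseline that predates therapy.
- **Other compartments.** Overall PR also depends on skin, blood, liver, spleen and new lesions, so reaching the target-lesion threshold is not enough. This stands, and the table above does not model it.
- **Descriptive analysis.** Section 5.1 calls the analysis primarily descriptive, and sensitivity to one patient is common to any single-arm trial of 18. This also stands. That sensitivity is not evidence about the scan window.
- **Carry-over remains.** Therapy on day -35 with a scan on day -34 would pass the proposed sentence, while a scan on day -36 would not, although the carry-over is nearly the same. This is correct and limits what can be claimed for the fix.

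**Conclusion.** The ordering gap is real and follows from the dates alone: a scan from as early as day -41 can be the baseline for a patient treated up to day -29. The exception creates it, and no other section closes it. For an affected patient, prior shrinkage of 10% to 30% lowers the further reduction needed for target-lesion PR from 50% to between 44.4% and 28.6%.

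Three stronger readings are tempting, and the documents support none of them:
- **That the false-success figures measure the benefit of the fix.** They rest on assumed exposure and carry-over, and delayed effects of therapy given before the scan remain under any version of the rule.
- **That the exception inflates ORR overall.** Growth after an old scan can hide a response, so the net direction is unknown.
- **That the fix gives a clean baseline.** It corrects the order of scan and therapy and nothing else.

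This is an inexpensive improvement to consider. It does not change the sample size, the derived 4-of-18 rule or the power.

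**What to change.** Add to section 2.6.1 and Appendix D: a tumor assessment from outside the 28-day window is accepted as baseline only if it was made after the last prior anti-cancer therapy and any radiotherapy; otherwise it is repeated within the window.

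With this sentence, the 12 days on which permitted therapy could follow a day -41 scan fall to 0. Only scans from about day -41 to day -29 are touched, and washouts and eligibility stay as written. The cost is one sentence and an occasional repeat screening scan.

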#### **2.6.2 Baseline Assessments on Cycle 1 Day 1 (C1D1)**

Baseline assessments include a complete physical examination, vital signs, ECOG performance status, weight, concomitant medications, laboratory tests (hematology, chemistry, coagulation, and urinalysis), and safety ECG. Women of childbearing potential must have a negative pregnancy status confirmed by serum test before dosing. If Serum pregnancy test result cannot be obtained on the same day before dosing, urine pregnancy test should be conducted additionally and the result should be confirmed before dosing (see [Appendix A](#)). Some of the pre-dose assessments except vital signs and ECG may be performed 1 day before C1D1 to accommodate scheduling requirements in the hospital.

#### **2.6.3 Treatment Phase**

All assessments must be performed as per the Schedule of Events (see [Appendix A](#)). Assessments scheduled on the day of study treatment should be performed prior to taking study drug, unless otherwise noted in the schedule of assessments.

Assessment of tumor response will be scheduled by end of the fourth week, eighth week, then every 8 weeks ( $\pm$  1 week) from C3D1. However, if a patient develops clinical signs and symptoms of PD, or unacceptable toxicity occurs, tumor assessment may be performed sooner as needed.

#### **2.6.4 End of Treatment Safety Follow-up Visit**

All patients receiving at least 1 dose of HBI-8000 and discontinuing treatment for any reason except death will be evaluated approximately 30 ( $\pm$  3) days after the last dosing of study drug or before the initiation of new cancer treatment, whichever is earlier. Any patient for whom study treatment has been discontinued should complete study procedures listed in the EoT visit. At EoT safety visit, evaluations will include physical examination, vital signs, body weight, ECOG performance status, hematology, blood chemistry, urinalysis, pregnancy test (if applicable), ECG, and assessment of any ongoing AEs. If a patient discontinues study

treatment before PD is recorded, and if the last tumor assessment was >30 days earlier from the EoT visit, tumor assessment should be performed at EoT. In these patients, further tumor assessments are to be performed approximately every 3 months  $\pm$  2 weeks until PD or the start of new cancer therapy whichever occurs first, unless consent to study participation is withdrawn.

Patients with HBI-8000-related AEs of Grade  $\geq$  2 observed at the EoT visit should be followed-up and monitored monthly (phone calls/clinic visits) until the AEs have resolved to Grade  $\leq$  1 or are determined to be chronic, or patient receives other anti-cancer therapy.

#### **2.6.5 Survival Follow-up**

Follow-up for survival (and tumor status in patients in whom PD has not yet been observed) should occur at approximately 3 month intervals after the EoT visit. Survival status may be conducted every 3 months  $\pm$  2 weeks by telephone contact or e-mail until death or end of study, defined as 12 months after the administration of the last dose of the entire study. The first subsequent anti-cancer therapy during this survival follow-up period should be recorded with regimen and start date in the appropriate Electronic Case Report Form (eCRF).

#### **2.6.6 Patient Withdrawal**

Patients have the right to withdraw from the study at any time for any reason, and the investigator should try to ascertain the reason for withdrawal as completely as possible. The investigator also has the authority to decide whether a patient should be discontinued from the study. Study treatment may be discontinued and the patient withdrawn from the study under the following circumstances:

- Unacceptable toxicity (AE)
- Progression of the disease under study
- Decision by the investigator to permanently discontinue study drug administration
- Intercurrent illness that would, in the judgment of the investigator, affect clinical assessments, patient safety, or follow-up significantly
- Significant protocol deviations that jeopardize the usefulness of the data
- Repeated patient non-compliance
- Patient is beginning another anti-cancer treatment protocol
- Patient becomes pregnant
- Patient requests to withdraw informed consent
- Study termination by the sponsor

All patients who withdraw from study treatment must complete an EoT visit, to be performed  $30 \pm 3$  days after the last dosing of the study drug (see [Appendix A](#)) or before the initiation of

new cancer treatment, whichever is earlier. A patient may withdraw consent for treatment but still allow follow-up, in which case he/she should be followed for safety, survival, and disease status. If a patient has withdrawn consent to study participation entirely, no subsequent follow-up will be performed.

Patients who are lost to follow-up or withdraw consent for study participation prior to receiving HBI-8000 or who withdraw before completing Cycle 1 for reasons unrelated to drug AEs or PD will be replaced.

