## 2.6 Study Procedures Overview

Patients may be treated in this study as long as they receive clinical benefit (SD or a response) in the absence of unacceptable toxicity. Progressive disease would be determined by investigators based on local radiology findings and clinical judgement. No independent radiology review is required prior to designation of PD and treatment discontinuation. Independent Radiology Review and Independent Overall Efficacy Review will be performed for final efficacy analyses at the completion of this study.

To ensure patient safety, a data safety monitoring board (DSMB) will convene to review the cumulative safety profiles of study patients at following milestones: first 6 patients completing at least 1 cycle, 12, 18, 30 patients have been treated for at least 1 cycle; and at end of treatment (EoT) phase of the study. Based on the observed safety, dose and regimen of ongoing treatment may be modified as needed. For all patients, weekly safety laboratory tests will be obtained during the first 28 days and closely monitored for safety signals, especially the neutropenia and transaminase elevation.

It is estimated that each patient will be on study for up to 12 months after enrollment. Assuming that 24 months are needed to meet accrual target, the study period would be of 36 months to allow efficacy and safety determination. After study drug is discontinued, patients will be followed as described in [Sections 2.6.4](#) and [2.6.5](#).

Patients will be screened by the study site investigator prior to entry into the study. Patients will receive a detailed explanation of the study design, and the potential risk/benefit of treatment will be disclosed to patients prior to the screening process. Only eligible and consenting patients will be enrolled in the study. The investigator will maintain a screening log to record all patients screened.

Local radiology reports on disease status will guide investigator's decision on-study treatment, including discontinuation. At the end of the study, tumor response of each patient will be reviewed by independent radiologists and oncologists in a blinded fashion to obtain best response, dates of response and progression. The data from independent and local assessment will be analyzed in parallel in final study report.

The Schedule of Events is presented in [Table 4](#) of [Appendix A](#) (Section 9.1).

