### **5.5.3 Patient Disposition**

Data tabulations will summarize the following patient numbers:

- Enrolled
- HBI-8000 treatment dose received
- Evaluable for safety and efficacy
- Protocol violations
- Protocol completions
- Withdraw from study due to:
  - AE
  - Physician's recommendation
  - Withdrew consent
  - Lost to follow-up
  - Other reasons as collected on the eCRF

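### Section 2.6.6 lets the investigator withdraw patients from the study, not only from treatment, on grounds linked to prognosis, while other sections require their follow-up to continue; OS, and PFS for exits before progression, may be biased.

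*Combined protocol and SAP*

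**What the plan says.** **Text that permits leaving the study.** Section 2.6.6 opens its list of ten grounds with "Study treatment may be discontinued and the patient withdrawn from the study under the following circumstances". The grounds include unacceptable toxicity, progression, intercurrent illness, significant protocol deviations, repeated non-compliance and starting another anti-cancer protocol. Just before the list it adds: "The investigator also has the authority to decide whether a patient should be discontinued from the study". Section 5.5.3 plans a disposition count headed "Withdraw from study due to", with AE and physician's recommendation among the reasons. Section 5.10.1 names discontinuation of treatment and withdrawal from the study as alternative outcomes of a TEAE.

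**Text that requires follow-up.**
- Section 2.6: "After study drug is discontinued, patients will be followed as described in" Sections 2.6.4 and 2.6.5, with no exception by reason.
- Section 2.6.4: a patient who stops the drug before progression has further tumor assessments "until PD or the start of new cancer therapy whichever occurs first, unless consent to study participation is withdrawn".
- Section 2.6.5, repeated in note c of Table 4: survival contact runs "by telephone contact or e-mail until death or end of study, defined as 12 months after the administration of the last dose of the entire" trial.
- Section 2.6.8: after unacceptable AEs recur despite two dose reductions, treatment stops for good and post-treatment follow-up begins.

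**Text that separates the two ideas.** The end of 2.6.6 says: "A patient may withdraw consent for treatment but still allow follow-up, in which case he/she should be followed for safety, survival, and disease status". It then says that nothing further is collected once consent to participation is fully withdrawn.

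**The concern.** Stopping the drug and leaving the study are different events. The first should not affect whether PFS and OS are observed; the second ends observation. Section 2.6.6 joins them in one permission and leaves its use to the investigator, at 25 to 35 sites that together enroll about 22 patients. Two sites could therefore handle the same event differently, and with so few patients one or two such cases can move a median.

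Section 5.9 summarizes PFS, DOR and OS by Kaplan-Meier, which is valid only if patients whose observation ends early have the same outlook as those who remain. Removal for toxicity, intercurrent illness or progression is plausibly related to outlook. Follow-up that was never collected cannot be restored at the analysis stage.

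**Working it through.** **Step 1. The passages side by side**

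| Event | Section 2.6.6 permits | Elsewhere required |
|---|---|---|
| Unacceptable toxicity, no PD | Withdrawal from the study | Tumor and survival follow-up (2.6, 2.6.4, 2.6.5); follow-up after recurrent toxicity (2.6.8) |
| Repeated non-compliance, no PD | Withdrawal from the study | Tumor and survival follow-up (2.6, 2.6.4, 2.6.5) |
| Progression | Withdrawal from the study | Survival follow-up to death or end of study (2.6.5; Table 4, note c) |
| Starting another anti-cancer protocol | Withdrawal from the study | Survival follow-up, with the first subsequent therapy recorded (2.6.5) |
| Patient withdraws consent to treatment only | Follow-up continues | Same |
| Patient withdraws consent entirely | No follow-up | Same (2.6.4) |

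The last two rows agree and the first four do not. The protective sentence at the end of 2.6.6 covers only the patient's own withdrawal of consent to treatment, not removal by the investigator. The EoT visit that 2.6.6 requires secures one contact about 30 days after the last dose, not later follow-up.

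**Step 2. Which endpoints are exposed**
- *OS (exploratory):* any exit from the study before death.
- *PFS (secondary):* exits before progression. A patient removed for progression already has a PFS event on investigator assessment.
- *ORR (primary):* only if a patient leaves before response is assessed.

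**Step 3. Size, under assumptions**

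The plan gives no figure to reproduce: no rate of withdrawal from the study, no expected median OS and no hazard after withdrawal. Every input below is assumed.

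Inputs: exponential OS with median 6 months, so λ = ln 2 / 6 = 0.1155 per month. A share f = 0.20 is assigned to withdrawal at a time c uniform on 0.5 to 2 months, and from then on has hazard hλ. Suppose that these patients enter the analysis as censored at c.

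- *With censoring at withdrawal:* everyone under observation has hazard λ, so the Kaplan-Meier median is 6.0 months.
- *With full follow-up:* for t > 2 months, and with x = exp(−λt), S(t) = 0.8x + 0.2·E·x^h, where E is the mean of exp((h−1)λc). Set S(t) = 0.5 and solve.

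| h | E | Equation | x | True median = −ln(x)/λ | Overstatement = 6/median − 1 |
|---|---|---|---|---|---|
| 1 | 1 | x = 0.5 | 0.500 | 6.0 | 0% |
| 2 | 1.157 | 0.8x + 0.2314x² = 0.5 | 0.5405 | 5.33 | 13% |
| 3 | 1.342 | 0.8x + 0.2683x³ = 0.5 | 0.5646 | 4.95 | 21% |

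Large-sample simulation gives the same percentages. With f = 0.10 the overstatement is 3.5% at h = 1.5 and about 10% at h = 3.

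**Step 4. Two further illustrations, also with assumed values**
- *OS, exits at progression:* with median time to progression 3 months and median survival after progression 5 months, simulated median OS is 9.5 months with no exits. If 10%, 25% or 50% are censored at progression, it becomes 9.8, 10.3 or 11.6 months.
- *PFS, exits before progression:* with median PFS 3 months, 10% to 30% withdrawn between 0.5 and 3 months, and a later hazard 1.5 to 3 times higher, the true median ranges from 2.94 down to 2.59 months, while Kaplan-Meier still shows about 3.0.

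**The case against.** **The intent is clear from the rest of the protocol.** Section 2.6.4 covers stopping treatment for any reason except death. Section 2.6.5 mentions tumor status only for patients without PD, which implies that patients with PD are also followed for survival. Section 2.6.8 says that follow-up comes after recurrent toxicity. The wording in 2.6.6 is permissive, and it never says that follow-up ends for toxicity, progression or non-compliance. This stands in part: the likely intent was to stop treatment only. But 2.6.6 grants authority over study participation in plain words, and 5.5.3 and 5.10.1 plan to count its use, so the conflict is more than loose phrasing.

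**A reader might infer that 2.6.6 prescribes censoring at withdrawal, and so that the medians are biased upward.** The documents do not support that. The text contains no censoring rule for PFS or OS, and section 5.1 leaves detailed methods to an SAP. Nor do the documents show that withdrawn patients fare worse; with equal hazards the bias is zero.

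**A reader might also take a withdrawal rate from the plan's own figures.** Neither candidate is one. The 20% in section 5.2 allows for patients who do not complete treatment or evaluations needed for efficacy. The 2 of 6 in section 1.8 had transient, asymptomatic toxicities at 40 mg, and no withdrawal from the study is reported for them. The 20% used in the working is an assumption that happens to equal the first figure.

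**The primary result is hardly touched.** This stands. The primary endpoint is ORR, the analysis is mainly descriptive, and the main data cut-off comes once the last patient has had at least one efficacy assessment on study.

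**Conclusion.** The conflict is real and is in the current text. Section 2.6.6 allows removal from the study on grounds for which 2.6, 2.6.4, 2.6.5, 2.6.8 and Table 4 note c require continued follow-up. If sites use the permission, Kaplan-Meier OS may be biased, as may PFS for exits before progression.

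The size is unknown. It is nil if the hazard after withdrawal is unchanged, and about 13% to 21% on median OS under the assumed 6-month median, 20% early withdrawal and a later hazard 2 to 3 times higher. These are conditional illustrations, not estimates for this trial. Because a secondary and an exploratory endpoint are affected, the correction is advisable and does not call the primary analysis into question.

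**What to change.** 1. **Section 2.6.6, opening of the list:** limit it to discontinuation of study treatment and remove the reference to withdrawing the patient from the study. The listed grounds for stopping treatment stay unchanged.
2. **Section 2.6.6, investigator authority:** limit this sentence to discontinuing study treatment. If it is left as it stands, it contradicts the new text.
3. **Section 2.6.6, new sentence:** *Only death, withdrawal of consent to study participation, loss to follow-up or study termination ends follow-up; all other patients who stop study drug continue under Sections 2.6.4 and 2.6.5.*
4. **Section 5.5.3:** tabulate reasons for stopping treatment separately from reasons for leaving the study.

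The cost is a wording change in a protocol amendment and one table split in two. Section 2.6.5 already provides for the three-monthly contacts and 2.6.4 for the tumor assessments, so no procedure is added. The change is worth making while patients are being followed, because data lost during conduct may not be recoverable.
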